3.4 Expected Duration of Subject Participation

3.4.1 Duration of Therapy

In the absence of treatment delays or cessation due to adverse events, treatment may continue indefinitely or until one of the following criteria applies:

- Disease progression.
- Intercurrent illness that prevents further administration of treatment.
- The investigator considers it, for safety reasons, to be in the best interest of the patient. The investigator may recommend gradual discontinuation (i.e. ruxolitinib taper) in patients achieving a prolonged response (defined as a PR or CR ≥ 6 months in duration). The rate of a ruxolitinib taper, and decisions to dose escalate in the setting of recurrent signs/symptoms, are not specified in this protocol, and are at the discretion of the investigator.
- Unacceptable adverse events such as any toxicity or other issue that causes a delay of study drug administration by more than 4 weeks.
- General or specific changes in the patient's condition render the patient unacceptable for further treatment in the judgment of the investigator.
- Patient decision to withdraw from treatment (partial consent) or from the study (full consent).

- Death.
- Sponsor reserves the right to temporarily suspend or prematurely discontinue this study.

The date and reason for discontinuation must be documented. Every effort should be made to complete the appropriate assessments.

3.4.2 Duration of Follow Up

Patients will be followed for efficacy and toxicity for 30 days after treatment has been discontinued. Thirty days after treatment discontinuation, progression-free and overall survival will be collected every 6-12 months by a review of the clinical notes from the treating investigator or other provider. Patients will be followed for up to five years or until the end of the study or death, whichever occurs first.

Serious adverse events that are still ongoing at the end of the study period will necessitate follow-up to determine the final outcome. Any serious adverse event that occurs after the study period and is considered to be possibly related to the study treatment or study participation will be recorded and reported immediately per IRB & FDA reporting guidelines.

4. PATIENT SELECTION

A checklist will be used to confirm a patient's eligibility. The check list will include the inclusion and exclusion criteria listed below, and must be completed for each patient and must be signed and dated by the treating physician.

4.1 Inclusion Criteria

Patients must meet all of the following inclusion criteria to be eligible for enrollment:

1. Patients, or their legally authorized representative, must voluntarily provide written IRB-approved informed consent.
2. Males and females, 18 years of age or older at the time of enrollment.
3. Patients must meet the diagnostic criteria for HPS (at least 5 of the following):
 - fever
 - splenomegaly
 - cytopenia involving ≥ 2 cell lines (Hemoglobin < 9 g/dL; platelets $< 100,000/\mu\text{L}$; absolute neutrophil count $< 1000/\mu\text{L}$)
 - hypertriglyceridemia or hypofibrinogenemia
 - tissue demonstration of hemophagocytosis
 - low or absent NK cell activity
 - serum ferritin ≥ 3000 ug/L
 - soluble IL-2 receptor (CD25) > 2400 U/mL.
4. In the investigator's opinion, the patient has the ability to participate fully in the study and comply with all its requirements.

4.2 Exclusion Criteria

The presence of any of the following will exclude a patient from study enrollment.

1. CNS involvement
2. Malabsorption
3. Known secondary HPS that is otherwise treatable (e.g. non-Hodgkin's lymphoma).
4. Pregnant or lactating female: all females of child-bearing potential must have a negative serum pregnancy test within 7 days of treatment; lactating females must discontinue breast feeding.

5. Has received any prior systemic therapy, excluding corticosteroids, within 7 days (or 5 half-lives) of treatment.
6. Estimated creatinine clearance <15 mL/min
7. No active malignancy at the time of enrollment, except nonmelanoma skin cancers or carcinoma in situ. Patients with a prior history of malignancy are eligible if their malignancy has been definitely treated or is in remission and does not require ongoing adjuvant or cancer-directed therapies.
8. Active hepatitis B or hepatitis C or known HIV infection.
9. Known (and biopsy-confirmed) liver cirrhosis; or, a reported history of liver cirrhosis with a model for end-stage liver disease (MELD) score >20.

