1. INTRODUCTION

1.1 Hemophagocytic Syndrome

Hemophagocytic Syndrome (HPS) is a disorder characterized by pathological activation of the immune system resulting in a systemic disorder characterized by excessive cytokine production and macrophage activation, culminating in cytopenias and evidence of hemophagocytosis on tissue specimens. The disorder can be sporadic or familial due to one of several mutations and is primarily seen in the pediatric population, with a reported incidence of 1 case per 3000 admissions¹. The actual incidence in adults is unknown and can be rarely sporadic, or secondary to viral infections, malignancy, or autoimmune disease.

HPS is a universally fatal disease if untreated. In adults, the median survival has been reported to be less than 2 months if diagnosis and treatment is delayed². Adult patients are treated with pediatric protocols with early institution of etoposide and steroids and consolidation with allogeneic stem cell transplant in appropriately selected patients if a familial form is identified³. Other treatment strategies have been attempted, including rituximab⁴, infliximab⁵, entarcept⁶, tocilizumab⁷, and alemtuzumab⁸. These anecdotal reports highlight the therapeutic potential of cytokine-targeted therapies in this disorder.

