1.3 Background and Rationale

Hemophagocytic lymphohistiocytosis (HLH) or hemophagocytic syndrome (HPS) is an inflammatory disorder associated with the activation and expansion of reactive (i.e. non-clonal) macrophages. Primary HPS is associated with mutations (e.g. \approx 50% of familial cases are caused by perforin gene mutations) that culminate in defective natural killer (NK) cell and cytotoxic T-lymphocyte (CTL) degranulation and impaired killing of target cells. In these patients, a triggering event (e.g. viral infection) is associated with immune dysregulation that is characterized by the overproduction of proinflammatory cytokines (e.g. IL-12 and IFN- γ) and tissue accumulation of activated T-cells and macrophages.²⁷⁻³¹ These immunologic changes are associated with protean clinicopathologic manifestations, including: fever, hepatosplenomegaly, hyperferritinemia (due to macrophage activation), cytopenias (caused by phagocytosis - “hemophagocytosis”- of hematopoietic cells), hypofibrinogenemia, and multi-organ failure.³² Predominantly observed in children, primary HPS is initially managed with supportive care and chemotherapy, but is only curable in approximately 60% of children with allogeneic stem cell transplantation.^{3,33} In contrast to primary HPS, secondary HPS is more common in adults and is associated with a variety of triggers, including infection (often viral), autoimmunity, or hematologic malignancies (commonly non-Hodgkin lymphomas).³² For many patients, a precipitating cause cannot be identified. Apart from disease-specific therapies for patients in which a precipitating cause can be identified (e.g. non-Hodgkin lymphoma directed therapies for those with an underlying lymphoma), no HPS-specific therapies are currently available for the majority of adults with HPS. Therefore, these patients are frequently treated with a regimen originally developed for use in children with primary HPS that includes combinations of steroids, immunosuppressive agents (i.e. cyclosporine A), and etoposide. Not surprisingly, secondary HPS in adults is associated with high morbidity and mortality. In one of the largest single center studies, the overall mortality was 67%, with a median time from diagnosis to death of 35 (range: 5-160) days.² Therefore, improved therapeutic strategies for adults with secondary HPS are greatly needed.

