6.2 General Concomitant Medications and Supportive Care Guidelines

Because there is a potential for interaction of Ruxolitinib with other concomitantly administered drugs through the cytochrome P450 system, the case report form must capture the concurrent use of all other drugs, over-the-counter medications, or alternative therapies. The Principal Investigator should be alerted if the patient is taking any agent known to affect CYP3A4. In patients who concurrently take strong CYP3A4 inhibitors and a platelet count of at least 50,000 the dose of ruxolitinib should be capped at 10 mg twice daily due to the concern for increased serum concentrations of ruxolitinib's active metabolites. Strong CYP3A4 inhibitors, including grapefruit juice, should be avoided whenever possible.

Patients should receive full supportive care, including transfusions of blood and blood products, cytokines, antibiotics, anti-emetics, etc when appropriate.

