11.2 Rationale for Analysis

We will utilize immunofluorescent staining (by flow cytometry) to test the hypothesis that ruxolitinib inhibits Stat1 activation in HPS. We will evaluate the expression of Stat1 and pStat1 in peripheral blood T-cells and monocytes pre- and post-treatment. The post-treatment analysis will be conducted 7 (+/- 3) days following treatment initiation. T-cell (sIL-2R) and macrophage (soluble CD163) activation markers will be serially analyzed by ELISA in patient plasma. Plasma samples will be obtained weekly and cryopreserved for analysis of relevant cytokines (including interferon- γ) by ELISA. We will test the hypothesis that ruxolitinib decreases inflammatory markers (e.g. soluble CD163) associated with macrophage activation.

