Plasma will be obtained before treatment and weekly thereafter, and cryopreserved for future corollary studies (e.g. cytokine^{27,28} and soluble CD163 determination³⁴). We will compare cytokine, soluble IL-2R and soluble CD163 levels pre-treatment and post treatment. We seek to correlate change in expression (decrease) with positive response (complete vs. partial vs. stable) to therapy via regression models that appropriately account for the serial correlation of repeated measures within a patient. Inference from these models would be hypothesis generating.

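### The exploratory marker analyses credit any fall in inflammatory markers to ruxolitinib without using corticosteroid exposure, although steroids are exempt from the washout and unrestricted on study

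*Combined protocol and SAP*

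**What the plan says.** **Entry.** Section 4.2, exclusion 5, applies to a patient who "Has received any prior systemic therapy, excluding corticosteroids, within 7 days (or 5 half-lives) of treatment". The synopsis also exempts corticosteroids. Neither place gives a dose, a start date or a stable-dose condition.

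**During treatment.** Section 6.2 provides for full supportive care and does not mention corticosteroids. It does require that "the case report form must capture the concurrent use of all other drugs, over-the-counter medications, or alternative therapies"; the stated reason is cytochrome P450 interaction, and no analysis is said to use the record.

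**Steroids as treatment.** Section 1.1 states: "Adult patients are treated with pediatric protocols with early institution of etoposide and steroids". Section 1.3 describes the regimen often given to adults as one "that includes combinations of steroids, immunosuppressive agents (i.e. cyclosporine A), and etoposide".

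**Marker analyses.** Section 11.2 states: "We will test the hypothesis that ruxolitinib decreases inflammatory markers", with soluble CD163 as the example. Section 15.2 (Exploratory) states: "We will compare cytokine, soluble IL-2R and soluble CD163 levels pre-treatment and post treatment". It then relates the decrease to response category through regression models. The only feature specified for those models is that they allow for serial correlation within a patient. No steroid term, stratum, exposure table or sensitivity analysis is named. Section 15.2 calls inference from the models hypothesis generating.

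**The concern.** The trial has one arm, so the before/after change contains everything that changed around day 1. Corticosteroids are the one systemic therapy exempted by name from the washout, and the protocol itself counts them as HPS treatment. They are therefore the foreseeable co-treatment. If they are started or increased near the first ruxolitinib dose, they could lower the markers and could also produce the response. Section 13.1.3 grants a partial response for a 25% improvement in two or more quantifiable signs or laboratory markers. Steroid exposure is then a possible common cause in both exploratory analyses.

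What is at stake is the reading of the marker work. Followed as written, the plan could support its marker hypothesis when ruxolitinib has no effect on the marker. It could also show a marker-response association that steroid dosing helped to create.

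**Working it through.** **Plan's own figure.** There is none to reproduce. The documents give no test, sample size, SD or effect size for the marker comparison, and no steroid effect. What follows is an illustration.

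**Assumptions.** Paired t-test on log marker level, two-sided 5%. The number with a post-treatment sample is n = 8, out of the 10 patients planned in section 15.1. The SD of the log change is 0.5 to 0.8. Steroids lower the marker by 20%, 30% or 50% in newly exposed patients. The ruxolitinib effect is zero.

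**Formula when all patients are newly exposed.** The noncentrality is δ = ln(1 − fall) / SD × √n. The false-conclusion probability is P(T < −2.365), with T noncentral t on 7 degrees of freedom. With no steroid effect it is 2.5%. Example: for a 30% fall and SD 0.5, ln(0.7) = −0.357, so δ = −0.357 / 0.5 × √8 = −2.018 and the probability is 41.4%.

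**Partial exposure.** Each patient independently has a 25% or 50% chance of new exposure. These two columns were obtained by simulating the same test.

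| Steroid-driven fall | SD | δ (all exposed) | 25% exposed | 50% exposed | All exposed |
|---|---|---|---|---|---|
| 20% | 0.5 | −1.262 | 4.5% | 7.7% | 19.4% |
| 20% | 0.8 | −0.789 | 3.6% | 5.3% | 10.1% |
| 30% | 0.5 | −2.018 | 6.0% | 12.9% | 41.4% |
| 30% | 0.8 | −1.261 | 4.4% | 7.7% | 19.3% |
| 50% | 0.5 | −3.921 | 9.9% | 28.0% | 91.7% |
| 50% | 0.8 | −2.451 | 6.9% | 16.2% | 56.0% |

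The ranges are about 4-10%, 5-28% and 10-92%. The last is an upper bound, because it takes every patient as newly exposed.

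**Second check, n = 10.** The steroid-driven fall is set at 0.5, 1.0 or 1.5 SD of the change. The false-conclusion rate is 6%, 11% and 17% with 30% of patients exposed, 10%, 24% and 39% with half exposed, and 29%, 80% and 99% with all exposed. The pattern is the same.

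**Would restricting the main analysis to patients with no steroid dose increase solve it?** No, for two reasons.

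1. The pre-treatment draw falls within 48 hours of dosing (section 12.2). A patient who began steroids three days before day 1 and stayed on that dose would count as unchanged, with any steroid effect still developing.
2. The restriction selects on something that happens after treatment starts. Take n = 8, SD 0.65 and no effect of either drug. Suppose steroids are raised in 10% of patients whose markers fall. If they are raised in 50% of those whose markers rise, the false-conclusion rate in the retained patients is about 8%. If they are raised in 70%, it is about 15%. Both compare with 2.5%. The filter can create the error it is meant to remove.

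**The case against.** The strongest reply is that these analyses are exploratory, that section 15.2 already calls the model inference hypothesis generating, and that nothing decisive depends on them. That stands, and it is why the point is minor. The label is attached to the regression models, however, and does not soften the causal wording of the hypothesis in section 11.2.

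Other parts of the reply also stand:

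- Permission to start or raise steroids after day 1 is inferred from silence in section 6.2. Only steroid use before entry is expressly exempted.
- The documents never say that steroids lower sIL-2R, sCD163 or cytokines. They say only that steroids are part of HPS treatment.
- Steroids are one confounder among several. Natural history and regression to the mean also affect an uncontrolled before/after test. Soluble IL-2 receptor is itself a disease parameter in section 13.1.2, so its link with response is partly built in. Steroid tabulation repairs none of this.
- With 10 patients at most, and steroid dose possibly following the disease course, formal adjustment would be weak.

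A reader might infer three stronger things, and the documents support none of them. The first is that the survival result or the decision to continue is affected by this point; that decision rests on at least 4 of 10 patients alive at 2 months (sections 15.1 and 15.2), not on markers. The second is that the whole correlative programme fails; section 11.2 also plans a pStat1 test by flow cytometry, and nothing here shows that steroids affect it. The third is that a false ruxolitinib claim is likely; that depends on how many patients have new or increased steroids near day 1 and on the size of the steroid effect, neither of which the documents give.

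**Conclusion.** The concern holds as a minor point on the exploratory sIL-2R, sCD163 and cytokine analyses. The plan tests a ruxolitinib effect on these markers with an uncontrolled comparison, exempts from the washout a drug class that it describes as HPS treatment, and uses no steroid information in the analysis. A fall due partly to steroids could be credited to ruxolitinib.

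The size is conditional on the assumptions listed in the working. Partial exposure is the more useful guide, and there the inflation above 2.5% runs from slight to substantial. The all-exposed range should not be read as an expected error rate. The gap lies in the analysis plan, since section 6.2 already requires concurrent drugs to be recorded.

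**What to change.** In sections 11.2 and 15.2 (Exploratory):

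1. Keep all patients in the before/after comparison.
2. Tabulate each patient's corticosteroid start date and dose over time from the concomitant-medication record, and plot the markers against it.
3. Show marker change separately for patients with and without steroids newly started or increased shortly before or after day 1. State the window before the data are seen. Label this a sensitivity analysis, not the main set.
4. Unless the fall is also seen in patients without new or increased steroids, word the conclusion as change on ruxolitinib with or without corticosteroids, not as a ruxolitinib effect.
5. Do not make the subset with no dose increase the main analysis, and treat any time-varying steroid term in the models as descriptive only.

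The cost is a few sentences of plan text, steroid dose and dates on a form that section 6.2 already requires, a little more tabulation, and a more cautious exploratory conclusion. No new visit or sample is needed, and no change to who may receive steroids is proposed.

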4.3 Inclusion of Women and Minorities

Both men and women and members of all races and ethnic groups are eligible for this trial.

5. REGISTRATION

All subjects who have been consented are to be registered in an online Database. For those subjects who are consented, but not enrolled, the reason for exclusion must be recorded.

6. TREATMENT PLAN

6.1 Study Drug Administration

Appropriate dose modifications for Ruxolitinib are described in Section 7.0

Reported adverse events and potential risks of Ruxolitinib are described in Section 8.0.

TREATMENT REGIMEN DESCRIPTION					
Agent	Pre-medicate / Precautions	Dose	Route	Schedule	Cycle Length
Ruxolitinib	None	15 (mg)	PO in twice daily	Days 1-28	28 days

6.1.1 Ruxolitinib Administration

Patients will receive Ruxolitinib at 15 mg twice daily orally either on an empty stomach or with food for 4 weeks (28 days) in a 4 week (28 day) cycle. Ruxolitinib will be administered in continuous 28-day cycles. For patients unable to ingest tablets, ruxolitinib suspended in water may be administered through a nasogastric (NG) or percutaneous endoscopy gastrostomy (PEG) tube. Tablets should be suspended (1 tablet in ~40 mL water) in water and stirred for 10 minutes and administered within 6 hours of dispersion with an appropriate syringe. The NG or PEG tube should be rinsed with ~75 mL water following administration.

Ruxolitinib administration must be at least 1 hour before or after any other medications.

6.2 General Concomitant Medications and Supportive Care Guidelines

Because there is a potential for interaction of Ruxolitinib with other concomitantly administered drugs through the cytochrome P450 system, the case report form must capture the concurrent use of all other drugs, over-the-counter medications, or alternative therapies. The Principal Investigator should be alerted if the patient is taking any agent known to affect CYP3A4. In patients who concurrently take strong CYP3A4 inhibitors and a platelet count of at least 50,000 the dose of ruxolitinib should be capped at 10 mg twice daily due to the concern for increased serum concentrations of ruxolitinib's active metabolites. Strong CYP3A4 inhibitors, including grapefruit juice, should be avoided whenever possible.

Patients should receive full supportive care, including transfusions of blood and blood products, cytokines, antibiotics, anti-emetics, etc when appropriate.

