1.2.3 Clinical Pharmacokinetics

Twelve Phase I, five Phase II, and two Phase III clinical studies were conducted to explore the clinical pharmacology of ruxolitinib in healthy volunteers and in patients with MF, ET, PV, subjects with renal or hepatic impairment, prostate cancer, MM or rheumatoid arthritis (RA).

- Oral absorption of ruxolitinib is rapid and nearly complete, with $\geq 95\%$ absorption indicating high in vivo permeability in the human gastrointestinal tract, consistent with a Biopharmaceutical Classification System (BCS) Class I compound. Mean peak plasma concentrations (C_{max}) is achieved 1-2 h post-dose.
- The effect of food on ruxolitinib exposure is minimal and is not expected to be clinically significant; as a result, the drug may be administered either with or without food.
- Dose proportional exposure is observed between 5 and 200 mg dose range with linear pharmacokinetics (PK).
- Plasma protein binding is approximately 97% in vitro. There is moderate distribution to organs and tissues with no long-term retention of drug-related material in preclinical species and limited drug penetration into the central nervous system (CNS) or across the blood-brain barrier.
- There is $>95\%$ [¹⁴C] drug recovery in a mass balance study with 74% and 22% of the dose excreted in urine and feces of healthy subjects, respectively. Less than 1% of the administered dose is recovered in urine and feces as unchanged parent drug.
- The mean terminal elimination half-life is ~ 3 h with no appreciable accumulation of either parent or metabolites with twice daily dosing.
- Metabolism is predominantly via the cytochrome P450 isozyme CYP3A4 to yield oxygenated and subsequent conjugated metabolites.
- Oxidative metabolites of ruxolitinib retain pharmacological activity albeit with one half to one fifth of the activity of the parent compound. Ex vivo pharmacokinetic/pharmacodynamic (PK/PD) analysis indicates that the sum total of 8 active metabolites contribute to 18% of the overall PD activity of ruxolitinib.
- When administering ruxolitinib with strong CYP3A4 inhibitors, the total daily dose should be reduced by approximately 50%.
- No dose adjustment is necessary when co-administering ruxolitinib with strong CYP3A4 inducers.

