Both pre-clinical and clinical data highlight the central role of proinflammatory cytokines, particularly IFN- γ , that are dependent upon the JAK/STAT signaling in HPS pathogenesis.²⁷⁻³¹ The disease biology and clinical manifestations associated with HPS are driven by this underlying “cytokine storm”, culminating in T-cell accumulation and macrophage activation. Therefore, inhibition of JAK/STAT signaling may represent a novel therapeutic approach. As ruxolitinib inhibits upstream Janus kinases (JAK) at nanomolar concentrations, and is well tolerated in myelofibrosis patients (and alleviates signs/symptoms associated with hypercytokinemia), we sought to determine whether it inhibits STAT1 phosphorylation in IFN- γ treated macrophages. Not surprisingly, ruxolitinib (1 μ M) was able to inhibit STAT1 phosphorylation in treated macrophages. Therefore, ruxolitinib represents a novel therapeutic

approach for secondary HPS that has the potential to dramatically change the standard of care (and improve outcomes) for these patients. Cytopenias (including thrombocytopenia) observed in HPS are secondary to consumption (“hemophagocytosis”) and cytokine-mediated suppression, and are not secondary to underlying bone marrow “failure”. Therefore, treatment will be initiated at 15 mg po twice daily.

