7. DOSING DELAYS / DOSE MODIFICATIONS

Ruxolitinib will be dosed twice daily throughout the study. In the event a dose is missed, the subject should be instructed to take the next scheduled dose.

Dose Level	Ruxolitinib (BID schedule)	
	CrCl \geq 60	CrCl 15-59
Level 1 (starting dose)	15 mg	10 mg
Level -1 (reduction)	10 mg	5 mg
Level -2 (reduction)	5 mg	Hold

Event Name	Nausea
Grade of Event	Management/Next Dose for Ruxolitinib
\leq Grade 1	No change in dose
Grade 2	Hold until \leq Grade 1. Resume at same dose level.
Grade 3	Hold* until $<$ Grade 2. Resume at one dose level lower, if indicated.**
Grade 4	Off protocol therapy
*Patients requiring a delay of $>$ 4 weeks should go off protocol therapy.	
**Patients requiring $>$ two dose reductions should go off protocol therapy.	
Recommended management: antiemetics.	

Event Name	Vomiting
Grade of Event	Management/Next Dose for Ruxolitinib
\leq Grade 1	No change in dose
Grade 2	Hold until \leq Grade 1. Resume at same dose level.
Grade 3	Hold* until $<$ Grade 2. Resume at one dose level lower, if indicated.**
Grade 4	Off protocol therapy
*Patients requiring a delay of $>$ 4 weeks should go off protocol therapy.	
**Patients requiring $>$ two dose reductions should go off protocol therapy.	
Recommended management: antiemetics; in the event a dose of ruxolitinib is vomited, it is recommended that subjects resume ruxolitinib with the next scheduled dose.	

Event Name	Diarrhea
Grade of Event	Management/Next Dose for Ruxolitinib
≤ Grade 1	No change in dose
Grade 2	Hold until ≤ Grade 1. Resume at same dose level.
Grade 3	Hold* until < Grade 2. Resume at one dose level lower, if indicated. **
Grade 4	Off protocol therapy
*Patients requiring a delay of >4 weeks should go off protocol therapy. **Patients requiring > two dose reductions should go off protocol therapy.	
Recommended management: Loperamide antidiarrheal therapy Dosage schedule: 4 mg at first onset, followed by 2 mg with each loose motion until diarrhea-free for 12 hours (maximum dosage: 16 mg/24 hours) Adjunct anti-diarrheal therapy is permitted and should be recorded when used.	

Event Name	Thrombocytopenia
Platelet Count	Management/Next Dose for Ruxolitinib
50,000-100,000	Level 1 Ruxolitinib
35,000-49,999	Level -1 (reduction) if determined to be secondary to Ruxolitinib per the discretion of the investigator or PI.
20,000-34,999	Level -2 (reduction)

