Less than 20,000	Hold* until platelet count is at least 50,000 then resume at one dose level lower if determined to be secondary to Ruxolitinib per the discretion of the investigator or PI. Transfuse as needed for bleeds.
*Patients requiring a delay of >4 weeks should go off protocol therapy. **Patients requiring > two dose reductions should go off protocol therapy.	

Treatment will be discontinued for any patient that experiences a Grade 4 non-hematologic toxicity that is possibly related to ruxolitinib.

Dose adjustments for grades 1-3 non-hematologic toxicity that is possibly related to ruxolitinib will be at the discretion of the investigator or PI.

With the exception of thrombocytopenia (see table above), dose adjustments for grades 1-4 hematologic toxicity that is possibly related to ruxolitinib will be at the discretion of the investigator or PI.

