8.1.1 Ruxolitinib-related Adverse Effects

The following Ruxolitinib side effects are common (occurring in greater than 10%):

- Cardiovascular: Peripheral edema (22%), elevation in systolic blood pressure
- Central nervous system: Dizziness (15% to 18%), headache (10% to 15%), insomnia (12%)
- Dermatologic: Bruising (19% to 23%)
- Endocrine & metabolic: Cholesterol increased (17%; grade 2: <1%)
- Gastrointestinal: Diarrhea (23%), constipation (13%), nausea (13%), vomiting (12%)

- Hematologic: Anemia (96%; grade 3: 34%; grade 4: 11%), thrombocytopenia due to bone marrow suppression (70%; grade 3: 9%; grade 4: 4%), neutropenia (19%; grade 3: 5%; grade 4: 2%)
- Hepatic: ALT increased (25%; grades 2/3: 2%), AST increased (17%; grade 2: <1%)

The following Ruxolitinib side effects are less common (occurring in less than 10%):

- Respiratory: Dyspnea (16%), nasopharyngitis (16%)
- Gastrointestinal: Flatulence (5%)
- Genitourinary: Urinary tract infection (9%)
- Miscellaneous: Herpes zoster infection (2%)

The following Ruxolitinib side effects are rare:

- Cardiac murmur
- peripheral neuropathy
- weight gain
- progressive multifocal leukoencephalopathy (PML)
- Tuberculosis reactivation

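### With a strong CYP3A4 inhibitor, the 10 mg cap stops at platelets of 50,000, so at 35,000-49,999 an HPS-attributed count can leave a patient on 15 mg

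*Combined protocol and SAP*

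**What the plan says.** Section 6.2 sets the only inhibitor-specific dose in the treatment sections. For patients who take "strong CYP3A4 inhibitors and a platelet count of at least 50,000 the dose of ruxolitinib should be capped at 10 mg twice daily", the stated reason is concern about raised serum concentrations. The same section adds that "Strong CYP3A4 inhibitors, including grapefruit juice, should be avoided whenever possible" and that the principal investigator (PI) should be told of any agent that affects CYP3A4. It gives no dose for a strong inhibitor when platelets are below 50,000.

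Section 7 sets Level 1 at 15 mg twice daily for CrCl of 60 or more and at 10 mg for CrCl 15-59. Its thrombocytopenia table keeps Level 1 at 50,000-100,000. At 35,000-49,999 the instruction is "Level -1 (reduction) if determined to be secondary to Ruxolitinib per the discretion of the investigator or PI". At 20,000-34,999 it is Level -2 with no attribution clause. Below 20,000 it is "Hold* until platelet count is at least 50,000 then resume at one dose level lower if determined to be secondary to Ruxolitinib".

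Section 1.3 explains why the starting dose ignores the platelet count: "Cytopenias (including thrombocytopenia) observed in HPS are secondary to consumption" and cytokine-mediated suppression, not marrow failure. It concludes: "Therefore, treatment will be initiated at 15 mg po twice daily". Sections 4.1 and 4.2 set no platelet floor, and a count below 100,000 contributes to one of the diagnostic criteria. Background Section 1.2.3 says: "When administering ruxolitinib with strong CYP3A4 inhibitors, the total daily dose should be reduced by approximately 50" per cent, with no platelet condition.

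On response, Section 13.1.1 treats a patient as evaluable only after at least 7 days of therapy and a disease re-evaluation. Section 15.2 promises a count and percentage of responders without naming the denominator.

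**The concern.** A cap justified by drug exposure should not lapse as the platelet count falls. As written, two patients on the same inhibitor with the same renal function can be dosed in the wrong order: the one with fewer platelets may receive more drug. This runs against Section 7, which otherwise steps the dose down as the count falls.

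The hazard is plausible on the protocol's own account. Section 8.1.1 lists thrombocytopenia through marrow suppression in 70% of patients (grade 3 in 9%, grade 4 in 4%), so added exposure could act on a count that is already low. Low counts at entry are to be expected in this disease.

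The separate response point concerns who is counted. Section 1.3 cites a series in which time from diagnosis to death ranged from 5 to 160 days. A treated patient who dies or stops before day 7 can drop out of the response denominator.

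**Working it through.** The plan states no figure to reproduce here. The check reads Sections 6.2 and 7 together, by platelet band and renal column, for a patient on a strong CYP3A4 inhibitor.

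Inputs: the 6.2 cap (10 mg twice daily, platelets of at least 50,000); the Section 7 dose levels (CrCl 60 or more: 15, 10, 5 mg; CrCl 15-59: 10, 5 mg, hold); the Section 7 thrombocytopenia rows.

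Maximum twice-daily dose permitted:

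| Platelets | CrCl 60 or more | CrCl 15-59 |
|---|---|---|
| 50,000 or more | 10 mg (6.2 cap) | 10 mg (Level 1, equal to the cap) |
| 35,000-49,999, attributed to ruxolitinib | 10 mg (Level -1) | 5 mg (Level -1) |
| 35,000-49,999, not attributed to ruxolitinib | **15 mg** (no cap, no reduction) | 10 mg (Level 1) |
| 20,000-34,999 | 5 mg (Level -2) | hold (Level -2) |
| Below 20,000 | hold | hold |

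Only one cell exceeds the cell for a higher count. For example, with CrCl of 60 or more, a patient at 60,000 is limited to 10 mg, while a patient at 40,000 from HPS may take 15 mg.

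Size of the reversal:

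- Permitted daily dose in the band: 15 mg x 2 = 30 mg.
- Daily dose under the cap at a higher count: 10 mg x 2 = 20 mg.
- Ratio: 30 / 20 = 1.5.
- At CrCl 15-59: 10 / 10 = 1.0, so no reversal.

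The higher dose is not self-correcting. While the count stays at 35,000-49,999 and is attributed to HPS, the next blood count changes nothing.

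After removing the platelet condition from 6.2, the bold cell becomes 10 mg. The others are unchanged.

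Response denominator: let r be responders and k the number of the 10 treated patients who are not evaluable. The rate among evaluable patients is r / (10 - k); over all treated, with those patients as non-responders, it is r / 10. The first exceeds the second by a factor of 10 / (10 - k). The documents give no k. If k = 1 the factor is 10 / 9 = 1.11; if k = 2 it is 10 / 8 = 1.25.

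**The case against.** The strongest defence is that the 50,000 limit in 6.2 matches the lower edge of the Level 1 row in Section 7. On that reading 6.2 lowers Level 1 for inhibitor users and Section 7 takes over at lower counts. This works below 35,000. It fails at 35,000-49,999, because there the reduction depends on attribution to ruxolitinib and Section 1.3 expects the disease to be the cause.

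A second defence is that other text already protects the patient: strong inhibitors are discouraged, the PI is alerted, and Section 1.2.3 advises roughly halving the dose. These make the event less likely. But discouragement is not prohibition, an alert sets no dose, and the 1.2.3 advice is background that neither 6.2 nor 7 carries forward. If the sponsor meant that the combination should not be used below 50,000, the text does not say so.

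Third, harm is not demonstrated. None of the populations described in Section 8 has HPS, and ruxolitinib is intended to treat the process that lowers the count. That stands, and it limits the point to an inconsistent dosing rule with a plausible hazard.

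On response, one can say that a second denominator for a secondary endpoint in a 10-patient pilot is a reporting preference. That is fair as to weight, but the addition costs almost nothing.

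**Conclusion.** The dosing point holds within a narrow scope. It needs four conditions together: a strong inhibitor that cannot be avoided, CrCl of 60 or more, platelets of 35,000-49,999, and a low count not attributed to ruxolitinib. There the text permits 1.5 times the dose allowed at a higher count. The documents give neither baseline platelet counts nor expected inhibitor use, so the number of patients affected cannot be stated. The primary count of patients alive at 2 months, its decision rule and its analysis are unchanged.

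Three stronger readings are tempting, and the documents do not support them.

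- A reader might infer that 15 mg is allowed at any count below 50,000. Section 7 requires 5 mg or a hold below 35,000. Exposure there would arise only if the table did not govern first doses, and the protocol does not say that.
- A reader might infer that the excess lasts only until the first on-treatment blood count, due within 72 hours. In the firm scenario that count triggers no change, so a tally of doses over 72 hours does not describe it.
- A reader might set 30 mg a day against the halving in 1.2.3 (about 15 mg a day) and call the excess twofold. The operative standard is the 10 mg cap, and restoring it gives 20 mg a day, so 1.5 is the relevant ratio.

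The response-denominator point is separate and minor. It affects a secondary endpoint only.

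**What to change.** In Section 6.2, delete the platelet condition from the cap sentence. It would then say that any patient taking a strong CYP3A4 inhibitor receives at most 10 mg twice daily whatever the platelet count, and that a lower dose or a hold under Section 7 still applies. The sponsor's own 10 mg value stays. The cost is one clause, with no added patients, visits or data. The downside is a lower maximum dose for patients in the affected band who take a strong inhibitor.

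Separately, in Section 15.2, add a response rate over all treated patients, counting those with under 7 days of therapy as non-responders, beside the rate in evaluable patients. This needs no new data and may lower the reported rate.
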